2. Specific data to be collected through patient-reported questionnaires
 - a. Spontaneous Bowel Movement (SBM) frequency rate
 - b. Complete Spontaneous Bowel Movement (CSBM) frequency rate
 - c. Stool consistency (Bristol Stool Form Scale)
 - d. Straining (Ease-of-Passage Scale)
 - e. Abdominal discomfort (Self Assessment on 0–10-point numerical rating scale)
 - f. Bloating (Self Assessment on 0–10-point numerical rating scale)
 - g. Constipation severity (Self Assessment on 0–10-point numerical rating scale)
 - h. Overall relief (Self Assessment on 0–10-point numerical rating scale)
 - i. Balloon Expulsion Time (BET) before and after
 - j. Constipation symptom severity (PAC-SYM)
 - k. Constipation quality of life (PAC-QOL)
 - l. Need for rescue laxatives
3. Study endpoints – As above
4. Statistical methods
 - a. Analysis populations
 - i. Intent-to-treat (ITT) population: all patients who are randomized will be included in the ITT population. This will be the primary population for all analyses of demographics, patient characteristics and disposition, and efficacy data.
 - ii. Safety population: All patients who are randomized and receive any study treatment will be included in the safety population. This will be the primary population for all analyses of safety data
 - iii. Per-Protocol (PP) population: All patients who are randomized and receive the study medication on each day of their hospitalization. Major protocol violations include the following:
 1. Prohibited concomitant medication usage (specifically standing laxatives during hospitalization)The PP population may be used for supplementary analysis of selected efficacy and safety data, as appropriate.
 - b. Endpoint analyses
 - i. Primary endpoint: Colonic transit times will be compared in a paired fashion for individual patients before and after the intervention by means of a repeated measures ANOVA using a 3x2 design to distinguish between the outcomes of the three different groups. We will also use multivariable linear regression to compare change in transit time after adjusting for confounders, specifically: presence of IBS-C, abnormal balloon expulsion testing indicating dyssynergic defecation ($BET \geq 2$ minutes), age, and sex.

ii. Secondary endpoints: The secondary endpoints will be compared in a similar fashion, with logistic regression adjusting for confounders.

c. Power analysis

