This is a randomized, double-blind, single-center clinical exploratory pilot comparing treatment with CSP01 to standard control (CMC) to placebo (sucrose) for prevention of constipation in patients with chronic idiopathic constipation. Notably, there is no data either from the wireless motility capsule or from radio-opaque marker transit studies establishing a clinically-meaningful threshold for change in transit time in response to any colonic motility agent, and our hope is that transit data combined with patient-reported outcomes (our secondary endpoints) from this pilot study would provide a meaningful transit improvement threshold that may be used in future research as well. There is some data demonstrating the effect of dietary fiber on colonic transit time.⁷ If we extrapolate data from the trial of dietary fiber on colonic transit time, which demonstrated a 10-hour difference in colonic transit time with a standard deviation of 12 hours, we would assume the same effect for our standard fiber (CMC) group. Assuming that CSP01 would give an additional 3-hour decrease in colonic transit over conventional fiber, our current sample size would have 94% (with $\geq 90\%$ considered excellent) power to detect a difference. Even with 30 total subjects, we would still have 80% power (see graph below which varies the sample size).

Power Analysis/Sample Size Determination.
For a Repeated Measures Anova with Indicated Specifications, & Assuming
A Test-Retest Correlation of 0.7

If we are more conservative with the effect of CSP01 over standard fiber and decrease the additional effect to 1 hour decreased colonic transit time (1/3 of what

we would expect), we would still have 88% power with our current sample size.

VII. Risks and discomforts

1. Device side effects and adverse events

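### The 94% and 88% powers belong to the three-arm test; the CSP01-over-fiber difference they are tied to has about 14% and 6%, and no CSP01 contrast is named

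*Combined protocol and SAP*

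**What the plan says.** Section VI.4.c takes its effect size from a dietary fiber trial "which demonstrated a 10-hour difference in colonic transit time with a standard deviation of 12 hours", and for the comparator arm it says "we would assume the same effect for our standard fiber (CMC) group". It continues: "Assuming that CSP01 would give an additional 3-hour decrease in colonic transit over conventional fiber, our current sample size would have 94" per cent, described as "power to detect a difference. Even with 30 total subjects, we would still have 80% power". The arms between which the difference lies are not named in the text. The sensitivity case changes only the CSP01 increment: "If we are more conservative with the effect of CSP01 over standard fiber and decrease the additional effect to 1 hour", with 88% power reported. The caption of the power graph reads "For a Repeated Measures Anova with Indicated Specifications" and gives a test-retest correlation of 0.7.

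Section VI.4.b.i analyses the primary endpoint, colonic transit time, "by means of a repeated measures ANOVA using a 3x2 design to distinguish between the outcomes of the three different groups". It adds: "We will also use multivariable linear regression to compare change in transit time after adjusting for confounders". Neither sentence names a comparison of CSP01 with CMC or with placebo. Section II gives the purpose as the efficacy of CSP01 against both active control and placebo.

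**The concern.** The power paragraph introduces each figure with CSP01's advantage over fiber and then varies only that advantage. A reader will conclude that an advantage of 1 to 3 hours over CMC can be detected with 15 patients per arm. That is doubtful on its face: power drops only from 94% to 88% when the increment is cut by two thirds, so something else must be supplying the power.

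Two things are at stake. First, a significant three-arm test can arise from CMC alone, and the plan names no comparison that would separate this from a CSP01 effect. Second, if CSP01 merely matches CMC, a significant result says nothing about added benefit over fiber. That case is plausible, because Section VII.1 describes CSP01 as cross-linked CMC, although Sections I.c and VII.1 also give a mechanism by which it might do better. The protocol wants the transit data to inform a threshold for later research, so what the primary test shows needs to be clear.

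**Working it through.** **Inputs.** From the protocol: 15 per arm (IV.c); CMC-minus-placebo difference 10 h, SD 12 h, CSP01-minus-CMC difference 3 h or 1 h, correlation 0.7 (VI.4.c). Assumed: alpha 0.05, two-sided for pairwise tests, because the text states none and the graph is not available.

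**Step 1: SD of change.** 12 × √(2 × (1 − 0.7)) = 12 × √0.6 = 9.30 h; variance 86.4.

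**Step 2: reproduce the plan's figures.** With two time points, the group-by-time test is a one-way ANOVA on change, with noncentrality λ = n × Σ(arm mean − overall mean)² / 86.4. Arms are in the order placebo / CMC / CSP01, expressed as differences from placebo.

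| Scenario | n per arm | Σ of squares | λ | Power | Plan says |
|---|---|---|---|---|---|
| 0 / 10 / 13 | 15 | 92.67 | 16.09 | 94.3% | 94% |
| 0 / 10 / 11 | 15 | 74.00 | 12.85 | 88.2% | 88% |
| 0 / 10 / 13 | 10 | 92.67 | 10.73 | 79.8% | 80% |

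All three match. Alpha 0.025 would give 89.9%, 81.0% and 69.7%, and alpha 0.10 would give 97.3%, 93.6% and 88.2%, so the match supports 0.05. Using 12 h directly as the SD of change gives 77%, 67% and 57%; a baseline-adjusted SD of 8.57 h gives 97%, 93% and 86%. Neither fits. Adding a constant to every arm leaves λ unchanged, so nothing follows about the absolute placebo change.

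**Step 3: where the power comes from.** Change only the CSP01 arm, with 15 per arm:

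| Scenario | λ | Three-arm power |
|---|---|---|
| 0 / 10 / 10 (CSP01 equals CMC) | 11.57 | about 84% |
| 0 / 10 / 0 (CSP01 equals placebo) | 11.57 | about 84% |
| 0 / 10 / 7 | 9.14 | 74.6% |
| 0 / 10 / 5 | 8.68 | 72.2% |

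The λ present with no added CSP01 effect is 11.57/16.09 = 72% of the 3 h value and 11.57/12.85 = 90% of the 1 h value.

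**Step 4: pairwise power.** Noncentral t with 42 df; standard error of a difference 9.30 × √(2/15) = 3.39 h.

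| Comparison | Difference | Power |
|---|---|---|
| CSP01 vs CMC | 3 h | 13.9% |
| CSP01 vs CMC | 1 h | 6.0% |
| CSP01 vs placebo | 13 h | 96.3% |
| CSP01 vs placebo | 11 h | 88.6% |
| CSP01 vs placebo | 10 h | 82.1% |
| CSP01 vs placebo | 7 h | 52.2% |
| CSP01 vs placebo | 5 h | 30.2% |

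The 95% confidence interval half-width for any pairwise difference is 2.018 × 3.394 = 6.85 h. A pairwise difference must be about 9.7 h for 80% power. For scale only, 80% power for 3 h would take about 152 per arm.

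**Step 5: sensitivity.** For CSP01 vs CMC at 3 h, the alternative SDs in Step 2 give 10% to 15% (two-sided); one-sided testing at 0.05 gives about 22%. At 1 h the figures are about 6% two-sided and 9% one-sided.

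**Step 6: three-arm test, then CSP01 vs placebo only if it is significant** (simulation, 200,000 trials per scenario). Both steps are significant in 93.5% (13 h), 84.4% (11 h) and 77.7% (10 h). If CMC works and CSP01 equals placebo, the three-arm test is significant in about 84%, but both steps in only 4.9%.

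**The case against.** The strongest reply is that the power calculation matches the planned test. Section VI.4.b.i plans a 3x2 repeated measures ANOVA, the graph caption names a repeated measures ANOVA, and the figures reproduce with exactly that test. The text says only that a difference would be detected, and the CSP01 increment can be read simply as fixing the third arm's mean. The missing graph may list more. This stands in part: there is no arithmetic error, and the plan never says in words that CSP01 against CMC is the powered comparison. It does not remove the problem, because the text ties each power to an increment that contributes little to it, and no text says which arms are meant.

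It can also be said that no rule in the plan treats a significant three-arm test as success for CSP01, and that the arm means would expose an inert CSP01. That is fair, but reading the means after the fact is not a prespecified comparison, and the aim is about CSP01.

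Finally, this is an exploratory pilot, and CSP01 against placebo is well powered on the protocol's two scenarios. Both points lower the stakes. The second holds only if CSP01 delivers the full 10 h fiber effect plus the increment; power is about 52% at 7 h and 30% at 5 h.

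**Conclusion.** The concern holds and should be fixed. The stated 94%, 80% and 88% are correct for the three-arm group-by-time test, but they do not describe the ability to detect CSP01's added effect over fiber, which is about 14% for 3 h and 6% for 1 h. The three-arm test cannot by itself answer the aim in Section II: it would be significant about 84% of the time with an inert CSP01 and an effective CMC. The conclusion rests on the protocol's own SD, correlation and effect sizes and on an assumed alpha of 0.05, which reproduction of all three stated powers supports. The low power for CSP01 against CMC persists under every alternative SD tried and under one-sided testing.

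**What to change.** 1. In Section VI.4.c, state that 94%, 80% and 88% are powers of the three-arm group-by-time test under a 10 h CMC-minus-placebo difference, and state the alpha. Add the pairwise powers: CSP01 vs placebo 96% (13 h) and 89% (11 h), noting that these credit CSP01 with the full fiber effect; CSP01 vs CMC 14% (3 h) and 6% (1 h).
2. In Section VI.4.b.i, base the CSP01 efficacy conclusion on a named CSP01-minus-placebo contrast in change in colonic transit time. It can be the primary comparison, or a prespecified follow-up to a significant three-arm test, which keeps the planned ANOVA.
3. Have the adjusted regression report the same contrast, and report CSP01 vs CMC as an estimate with a 95% confidence interval.

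**Cost.** No extra patients, visits or measurements. The text changes need sponsor agreement and IRB approval as an amendment (IX.2 and IX.12). Keeping the three-arm test as a first step lowers power for CSP01 vs placebo from 96.3% to 93.5% at 13 h, from 88.6% to 84.4% at 11 h, and from 82.1% to 77.7% if CSP01 only equals CMC; making the contrast primary avoids that loss. The sponsor must also accept a much less favourable stated power against CMC, and say openly that the power against placebo rests on an extrapolated fiber effect.

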Given the in vitro performance of this novel, fiber-like hydrogel, it is therefore hypothesized that the device may be of benefit in patients with CIC and IBS-C, however, analysis of how it affects whole gut motility has not been conducted. This will be observed using wireless motility capsule (WMC) testing, a non-invasive diagnostic tool capable of measuring intraluminal pressure and pH through the whole GI tract, assessing both transit and contractility. WMC has been demonstrated as a safe, convenient, and reliable method of assessing whole gut transit after a dietary intervention in a more physiologic setting than traditional manometry or scintigraphy.

II. Specific Aims

This is a single center, randomized, double-blind, parallel-group, placebo-controlled pilot study. The purpose of the study is to evaluate the efficacy of the hydrogel capsule CSP01 vs active control (carboxymethylcellulose) vs placebo in accelerating colonic motility among patients with chronic idiopathic constipation. Patients who meet the Rome IV criteria for CIC or IBS-C and who meet the inclusion criteria will be offered participation in this study.

III. Subject Selection

This study aims to recruit 53 total subjects to be enrolled at one site, Massachusetts General Hospital. The 53 subjects that this study aims to recruit factors in a dropout rate of 15%, with a final sample size of 45 subjects.

INCLUSION/EXCLUSION CRITERIA:

Inclusion

1. Age 22-70 years old
2. BMI >18.5 and <35 kg/m²
3. Rome IV criteria for functional constipation or IBS-C
4. Continued IBS-C or CIC throughout Run-in period
5. Compliant with reporting during Run-in (confirm the presence of constipation during the 7-day Run-in baseline period; patients are required to report an average of <3 continuous spontaneous bowel movements [CSBMs] and ≤6 spontaneous bowel movements [SBMs] per week via the interactive web response system).

6. Ability to follow verbal and written instructions
7. Ability to record daily bowel habits, including frequency, stool consistency (BSFS), straining (EoPS), completeness of evacuation, and Patient Reported Outcomes (PROs) (abdominal discomfort, severity of constipation, bloating, overall relief)
8. Informed consent form signed by the subjects

Exclusion

1. History of loose stools
2. History of irritable bowel syndrome with diarrhea (IBS-D) or mixed irritable bowel syndrome (IBS-M)
3. Non-compliance with reporting during Run-in

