4. Patients reporting laxative, enema, and/or suppository usage for >2 days or any usage of a prohibited medication during the Run-in period
5. Patients reporting watery stools for any SBM (Type 7 on the Bristol Stool Form Scale [BSFS]) or loose (mushy) stools for >1 SBM (Type 6 on the BSFS) in the absence of laxatives during Run-in
6. GI motility obstruction or GI tract structural abnormality
7. Current use of prescribed or illicit opioids
8. History of pelvic floor dysfunction
9. Need for manual maneuvers in order to achieve a BM
10. History of GI lumen surgery at any time or other GI or abdominal operations within 60 days prior to entry into the study
11. History of high-dose stimulative or cathartic laxative abuse as judged by investigator team
12. Neurological disorders, metabolic disorders, or other significant disease that would impair their ability to participate in the study
13. Cardiovascular disease, diabetes, cancer, Crohn's disease, ulcerative colitis
14. BMI of <18.5 or >35 kg/m²
15. Pregnancy (or positive serum or urine pregnancy test(s) in females of childbearing potential) or lactation
16. Absence of contraception in females of childbearing potential
17. History of allergic reaction to carboxymethylcellulose, citric acid, sodium stearyl fumarate, raw cane sugar, gelatin, or titanium dioxide
18. Administration of investigational products within 1 month prior to Screening Visit
19. Exclusion of colonic inertia with symptoms of < 1 BM per 2 weeks
20. Subjects anticipating surgical intervention during the study
21. Known history of diabetes (type 1 or 2)
22. History of eating disorders including binge eating (except mild binge eater)
23. Supine SBP > 160 mm Hg and/or supine DBP > 95 mm Hg (mean of two consecutive readings)
24. Angina, coronary bypass, or myocardial infarction within 6 months prior to Screening Visit
25. History of swallowing disorders
26. Esophageal anatomic abnormalities (e.g., webs, diverticuli, rings)
27. History of gastric bypass or any other gastric surgery

28. History of small bowel resection (except if related to appendectomy)
29. History of gastric or duodenal ulcer
30. History of gastroparesis
31. History of abdominal radiation treatment
32. History of pancreatitis
33. History of intestinal stricture (e.g., Crohn's disease)
34. History of intestinal obstruction or subjects at high risk of intestinal obstruction including suspected small bowel adhesions
35. History of malabsorption
36. History of sucrose intolerance

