In addition to patients of MGH, subjects from the general greater Boston population will also be recruited. Subjects from the general population will be recruited through online advertisements run using the Galen Recruitment Service. Through this service, respondents will be filtered by qualifying questions. Contact information for qualified respondents will be provided to research study staff.

IV. Subject Enrollment

a.) Methods of enrollment

1. Patients may be approached by a research coordinator in the Neurointestinal Health clinic if they have a history of chronic constipation and agree to hear more about the trial
2. Patients may be called by the research coordinator prior to their appointment and asked if they would like to hear more about the trial
3. Any patients agreeing to hear more about the trial will learn more before beginning the informed consent process should they agree to participate as well as determining whether they meet all of the inclusion criteria
4. Patients may be contacted about the research study by their MGH physician on behalf of the research team. Afterward, patients may then be contacted by the research team directly.
5. Subjects who have provided their contact information through internet advertising may be contacted by the research team directly.

b.) Procedures for obtaining informed consent

1. Patients agreeing to participate will sign an informed consent with the study doctor at the time of enrollment, after proper informed consent has been provided by the site.

c.) Treatment assignment and randomization

1. Patients who have been enrolled and consented in the trial will be randomized with a ratio of 1:1:1 with 15 subjects per arm: 15 subjects on 3 capsules BID of CSP01, 15 subjects on 3 capsules BID (morning, evening) of carboxymethylcellulose (CMC), and 15 subjects on 3 capsules BID of placebo (sucrose).
2. We will stratify by Rome IV diagnosis of CIC vs. IBS-C to avoid clustering of IBS-C patients in one group.
3. The study personnel and patients will be blinded to treatment allocation.
4. Patients who fulfill study admission criteria and have a signed consent form will be assigned a 3-digit sequential patient number. The number will be used throughout the study.

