The protocol and any accompanying material to be provided to the patient (such as advertisements, patient information sheets, or descriptions of the study used to obtain informed consent) will be submitted by the investigator to the MGH IRB. Approval from the IRB must be obtained before starting the study and should be documented in a letter to the investigator specifying the protocol number, protocol version, protocol date, documents reviewed, and date on which the committee met and granted approval. Any modifications made to the protocol after receipt of IRB approval must also be submitted to the IRB for approval before implementation.

3. Informed consent

Written informed consent, in accordance with 21 CFR Part 50, must be obtained prior to participation in the study. Within the context of the inclusion criteria, a proportion of eligible patients may be exhibiting significant cognitive impairment and the lack of capacity to provide consent. As such, all patients will require surrogate consent by a legally authorized representative. The investigator or staff will determine the appropriate family member-person to contact regarding the study, based on the standard operating procedures of MGH and local and state laws. The signed consent form must remain in the patient’s medical chart and must be available for verification at any time.

4. Liability and insurance

The civil liability of the investigator, the persons instructed by the investigator and the hospital, practice, or institute in which they are employed, and the liability of the financial loss due to personal injury and other damage which may arise as a result of the carrying out of this study are governed by the terms and conditions set forth in the Clinical Trial Agreement and applicable law.

5. Documentation of study findings

Required information will be entered into the appropriate CRFs. All CRFs are to be completed accurately and promptly, and should be updated as needed so they reflect the latest information on the patient’s file. All records are to be kept in conformance with applicable guidelines and SOPs. When the study is completed, the investigator must retain the essential documents for as long as needed to comply with regulatory authority, local regulations and sponsor requirements further detailed in Section 10.2.5. The investigator shall notify the sponsor prior to moving or destroying any of the study documents.

6. Study monitoring

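### Section IX.3 requires surrogate consent for all patients, which does not fit the eligibility criteria and enrollment procedure under which the subject signs

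*Combined protocol and SAP*

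**What the plan says.** Three places in the combined protocol and SAP deal with who consents.

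- **Section IX.3 (Informed consent).** It first requires written consent before participation. It then says, with reference to the inclusion criteria, that "a proportion of eligible patients may be exhibiting significant cognitive impairment and the lack of capacity to provide consent". From this it concludes that "all patients will require surrogate consent by a legally authorized representative". The next sentence gives the procedure: "The investigator or staff will determine the appropriate family member-person to contact regarding the study", following hospital procedures and local and state law.
- **Section III, Inclusion criterion 8.** "Informed consent form signed by the subjects".
- **Section IV.b, item 1.** "Patients agreeing to participate will sign an informed consent with the study doctor at the time of enrollment".

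Three further criteria in Section III bear on the kind of person enrolled. Inclusion criterion 6 is "Ability to follow verbal and written instructions". Inclusion criterion 7 requires the ability to record bowel habits daily and to give patient-reported outcomes. Exclusion criterion 12 removes "Neurological disorders, metabolic disorders, or other significant disease that would impair their ability to participate in the study".

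**The concern.** The consent rule in Section IX.3 is operative text; it is neither background nor a description of superseded wording. Staff who follow it would seek a legally authorized representative for every patient, including an adult who is fully able to decide. Staff who follow Sections III and IV.b would take the subject's signature and stop there. Section IX.6 has monitors check adherence to the protocol, and the protocol gives them two different standards.

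Two things are at stake. The first is subject protection: who decides about participation should not depend on which section the staff read. The second is the implied population. Section IX.3 reads as though people without capacity to consent are eligible, in a trial that relies heavily on what subjects themselves record.

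**Working it through.** No arithmetic decides this point; the check is a comparison of the sections.

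**1. Who signs.** In Inclusion criterion 8, the subject. In Section IV.b, item 1, the patient, with the study doctor. In Section IX.3, a representative acting as surrogate, for all patients. Neither of the first two mentions a representative, and Section IX.3 does not say that the representative's consent is additional to the subject's.

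**2. Whether Section IX.3 follows from its own premise.** The premise concerns a proportion of eligible patients and the conclusion concerns all of them. Doubtful capacity in some patients could support a rule for those patients. It does not support one for everyone.

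**3. Whether the premise matches the inclusion criteria it invokes.** No inclusion criterion describes cognitive impairment. Criterion 1 sets an age range of 22 to 70. Criteria 6 and 7 require following instructions and daily self-recording, and Exclusion criterion 12 points the same way. Section V.a also has subjects complete a web-based daily diary and the PAC-SYM and PAC-QOL questionnaires. Recruitment (Sections III.c and IV.a) is directed to the patients themselves, by letter, telephone, clinic approach and online advertisement.

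**4. How far the endpoints depend on self-report.** Section V.c lists twelve secondary endpoints, a to l. Ten are the subject's own reports: spontaneous and complete spontaneous bowel movement rates, stool consistency, straining, abdominal discomfort, bloating, constipation severity, overall relief, PAC-SYM and PAC-QOL. The other two, balloon expulsion time and need for rescue laxatives, are not counted here. The primary endpoint, colonic transit time, comes from the motility capsule and is not self-reported.

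**5. How many people the rule touches.** The wording covers all patients, and that is as far as the documents go. Section III gives a target of 53, built from 45 completers and 15% dropout (45 / 0.85 = 52.9, rounded up to 53). The Schedule of Events puts consent at Day -28 to -15 and allocation at Day 0, with run-in exclusions between them. The documents do not say how many people will sign consent.

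**The case against.** The strongest reply is that the sections can be satisfied together. Inclusion criterion 8 and Section IV.b require the subject's signature but do not call it sufficient, and Section IX.3 does not say that the subject does not sign. With two signatures, all three are met. This stands as far as it goes: a breach is not unavoidable. It does not remove the problem. A surrogate ordinarily acts in place of the subject, no section provides for a second signature, and even on this reading nobody could join on their own signature alone.

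A second reply is that the enrollment procedure is clear, and that Section IX.3 looks like text carried over from an inpatient study. The per-protocol definition in Section VI.4.a refers to hospitalization and Section IX.9.b to a hospital chart, although this trial runs through clinic visits. That origin is plausible but is an inference. It would explain the sentence without making it harmless.

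Third, Section IV.c, item 6, mentions patients' representatives. That item concerns blinding and creates no consent role.

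A reader might infer more than the documents support:

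- **That all 53 consents would be deviations.** The 53 is a recruitment target and not a count of consents, and the two-signature route exists.
- **That people without capacity were enrolled, or that consent was defective.** Nothing in the documents shows which signatures were obtained. The consent pages are not in the reviewed text, so the signature block cannot be checked.

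**Conclusion.** The point holds as an internal inconsistency in which Section IX.3 is wrong as written. It extends a premise about some patients to all of them, invokes inclusion criteria that do not describe such a population, and does not fit the two places where the subject signs. As worded, the rule applies to every patient.

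It does not touch randomization, endpoints, analysis, power or sample size. Its weight lies in subject protection and in clarity about who is eligible.

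One assumption should be explicit. The protocol has no criterion that requires capacity to consent. That the intended population has capacity is inferred from Inclusion criteria 6 and 7 and Exclusion criterion 12. The inference is well supported, but the protocol should state the requirement.

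**What to change.** Reconcile Section III, Section IV.b and Section IX.3:

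- Delete from Section IX.3 the three consecutive sentences on cognitive impairment, surrogate consent and choosing a family contact.
- State there that each subject must have the capacity to consent and gives written consent personally, in line with Inclusion criterion 8 and Section IV.b, item 1.
- Make capacity an explicit eligibility requirement in Section III. Deleting the surrogate text alone would leave it only implied.

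The cost is a short wording amendment. Notifying the IRB would not be enough: Section IX.2 requires IRB approval before a modification is implemented, and Section IX.12 requires sponsor approval as well as prior approval of amendments submitted to the IRB. Data collection and sample size do not change.
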